8.2.1.4. Biomarkers

The Biomarker analysis set will include all subjects who have evaluable biomarkers data.

8.2.2. Data Handling Conventions

For the primary endpoint missing data will be handled using a missing = failure approach, unless otherwise specified.

For key secondary safety endpoints, missing data will be handled via a Last Observation Carried Forward (LOCF) method.

[figure not shown]
For other categorical secondary efficacy endpoints, missing data will be handled using a missing = failure approach. For the drug resistant mutations endpoint, a missing = excluded approach will be employed.

Sensitivity analyses will be performed as warranted.

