The efficacy of TDF in viremic treatment experienced CHB populations has been shown to be similar to treatment naïve subjects. In a prospective, randomized (1:1), double-blind, Phase 3b study (GS-US-174-0121) which compared TDF alone to the combination of FTC/TDF in 280 HBeAg-positive and HBeAg-negative subjects receiving treatment with LAM and having HBV DNA $> 3 \log_{10}$ IU/mL with documented LAM-resistance (rtM204I/V \pm rtL180M mutation[s]), 89.4% of TDF-treated subjects vs. 86.3% treated with FTC/TDF had HBV DNA < 69 IU/mL at Week 96 (primary endpoint, missing equals failure analysis; $p = 0.43$). BMD was also assessed in GS-US-174-0121, and small declines in BMD ($< 2\%$) of both hip and spine were seen with equal frequency in both groups which occurred by Week 24 (spine) and Week 72 (hip). In another prospective, randomized, double-blind study of TDF vs. FTC/TDF in 105 HBeAg-positive and HBeAg-negative subjects with a prior suboptimal response to ADV (GS-US-174-0106), no differences in HBV DNA suppression (proportion less than 69 IU/mL) were seen between treatment groups (82.4% TDF vs. 84.0% FTC/TDF; ITT, non-completer equals failure; $p = 0.78$). Taken together, these studies support the efficacy of TDF in treatment experienced subjects as being similar to results seen in treatment naïve subjects.

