8.6.1. Key Secondary Safety Analyses

The percent change from baseline in hip and spine BMD at Week 48 will be analyzed using an ANOVA model. The model will include treatment group as fixed effect. The details are provided in the Statistical Analysis Plan (SAP).

The change from baseline in serum creatinine at Week 48 will be analyzed using an ANCOVA model with baseline serum creatinine as a covariate, and treatment group as a fixed effect. The details are provided in the SAP.

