3.5. Missing Data and Outliers

3.5.1. Missing Data

A missing datum for a given study analysis window may be due to any of the following reasons:

- A visit occurring in the window but data were not collected or were unusable
- A visit not occurring in the window
- A subject permanently discontinuing from the study before reaching the window

For the primary endpoint and the secondary efficacy endpoints involving proportions, missing data will be handled using M = F approach. Sensitivity analyses will also be performed including an analysis excluding all missing data.

For the 3 key secondary safety endpoints (percentage change from baseline in hip BMD at Week 48, percentage change from baseline in spine BMD at Week 48, change from baseline in serum creatinine at Week 48), an analysis will be performed using the last observation carried forward (LOCF) method to impute missing data.

For the remaining endpoints, values for missing data will not be imputed, unless specified otherwise.

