7.3. Bone Safety Analyses

7.3.1. Bone Mineral Density (BMD)

For BMD analysis during the double-blind phase, any available on-treatment record on or prior to Open-label Study Day 14 will be included into the double-blind phase summary for those who enter the open-label phase after completion of the double-blind phase.

Percentage change from baseline in hip BMD and spine BMD will be summarized by treatment group and visit using descriptive statistics for subjects in the Hip and Spine DXA Analysis Sets, respectively.

Missing values for hip and spine BMD will be imputed using LOCF up to Week 96 for the analyses of percentage change from baseline. The last on-treatment postbaseline observation will be carried forward to impute the missing value. Baseline observation will not be carried forward.

Percentage change from baseline in observed hip and spine BMD will be analyzed similarly provided up to Week 96.

Observed BMD values will be used for all the analyses described below:

For each subject and each visit, the clinical BMD status will be defined for hip and spine BMD based on the corrected t-score in Table 7-1.

Table 7-1. Normal, Osteopenia, and Osteoporosis as Defined by T-score

Clinical Status	BMD T-score
Normal	t-score \geq -1.0
Osteopenia	$-2.5 \leq$ t-score $<$ -1.0
Osteoporosis	t-score $<$ -2.5

The number and percentage of subjects in each clinical BMD status (normal, osteopenia, and osteoporosis) will be summarized by visit and by baseline clinical status for both hip and spine.

For each subject and each visit, percentage change from baseline in hip BMD and spine BMD will be classified into 10 categories: $> 7\%$ decrease, $> 5\%$ to $\leq 7\%$ decrease, $> 3\%$ to $\leq 5\%$ decrease, $> 1\%$ to $\leq 3\%$ decrease, > 0 to $\leq 1\%$ decrease, 0 to $\leq 1\%$ increase, $> 1\%$ to $\leq 3\%$ increase, $> 3\%$ to $\leq 5\%$ increase, $> 5\%$ to $\leq 7\%$ increase, and $> 7\%$ increase. The number and percentage of subjects in each category will be summarized by visit.

Median (Q1, Q3) and mean (95% CI) of percentage change from baseline in observed hip and spine BMD over time will be plotted by treatment group. Listings of hip and spine DXA results will be provided.

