47.8.5	Summary of Fasting Total Cholesterol to HDL Ratio at Baseline and Week 48 (Excluding Subjects Taking any Lipid Modifying Medication)	Safety Analysis Set
48.1.1	Percentage Change from Baseline in Hip Bone Mineral Density by Visit (LOCF Imputation)	Hip DXA Analysis Set
48.1.2	Percentage Change from Baseline in Hip Bone Mineral Density by Visit (Observed Data)	Hip DXA Analysis Set
48.2.1	Percentage Change from Baseline in Spine Bone Mineral Density by Visit (LOCF Imputation)	Spine DXA Analysis Set
48.2.2	Percentage Change from Baseline in Spine Bone Mineral Density by Visit (Observed Data)	Spine DXA Analysis Set
49.1	Clinical Hip Bone Mineral Density Status by Baseline Status and Visit	Hip DXA Analysis Set
49.2	Clinical Spine Bone Mineral Density Status by Baseline Status and Visit	Spine DXA Analysis Set
50.1	Gradation of the Percentage Change in Hip Bone Mineral Density by Visit	Hip DXA Analysis Set
50.2	Gradation of the Percentage Change in Spine Bone Mineral Density by Visit	Spine DXA Analysis Set
51.1	Bone Biomarkers: Summary of Serum C-type Collagen Sequence (CTX, ng/mL) by Visit	Safety Analysis Set
51.2	Bone Biomarkers: Summary of Serum Bone Procollagen Type 1 N-terminal Propeptide (P1NP, ng/mL) by Visit	Safety Analysis Set
51.3	Bone Biomarkers: Summary of Serum Parathyroid Hormone (PTH, pg/mL) by Visit	Safety Analysis Set
51.4	Bone Biomarkers: Summary of Osteocalcin (OC, ng/mL) by Visit	Safety Analysis Set
51.5	Bone Biomarkers: Summary of Bone Specific Alkaline Phosphatase (bsAP, ug/L) by Visit	Safety Analysis Set
52	Treatment-Emergent Fracture Events	Safety Analysis Set
53.1.1	Summary of 10 Year Probability of Hip Fracture (%) by Visit (Age \geq 40 Years)	Hip DXA Analysis Set
53.1.2	Summary of 10 Year Probability of Hip Fracture (%) by Visit (All Subjects)	Hip DXA Analysis Set
53.2.1	Summary of 10 Year Probability of Major Osteoporotic Fracture (%) by Visit (Age \geq 40 Years)	Hip DXA Analysis Set
53.2.2	Summary of 10 Year Probability of Major Osteoporotic Fracture (%) by Visit (All Subjects)	Hip DXA Analysis Set
54	Treatment-Emergent Bone Events	Safety Analysis Set
55	Treatment-Emergent Confirmed Renal Laboratory Abnormality	Safety Analysis Set
56.1	Summary of Serum Creatinine (mg/dL) by Visit (LOCF Imputation)	Safety Analysis Set
56.2	Summary of Serum Creatinine (mg/dL) by Visit (Observed Data)	Safety Analysis Set

Table Number	Title	Analysis Set

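### A missing Week 48 BMD value is filled with a Week 24-window scan; at the hip this may misstate Week 48 loss, by a small amount and in a direction not established, and a repeated-measures model on the same scans avoids it

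*Protocol*

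**What the plan says.** Protocol 8.2.2 sets the rule for all three key secondary safety endpoints: "For key secondary safety endpoints, missing data will be handled via a Last Observation Carried Forward (LOCF) method". SAP 3.5.1 repeats it in softer terms ("an analysis will be performed using the last observation carried forward (LOCF) method to impute missing data"), and SAP 7.3.1 gives the BMD detail: "The last on-treatment postbaseline observation will be carried forward to impute the missing value. Baseline observation will not be carried forward".

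For the model, Protocol 8.6.1 plans a single-visit ANOVA of Week 48 percent change: "The model will include treatment group as fixed effect". It names no other term and refers to the SAP for details. The SAP supplied covers only the China Week 48 analysis and summarises BMD descriptively.

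The SAP pairs the imputed results with unimputed ones: "Percentage change from baseline in observed hip and spine BMD will be analyzed similarly". Appendix 1 lists Table 48.1.2, "Percentage Change from Baseline in Hip Bone Mineral Density by Visit (Observed Data", and Table 48.2.2 for the spine.

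On the time course, Protocol 1.3.2 describes small BMD declines in an earlier study of TDF against FTC/TDF, "which occurred by Week 24 (spine) and Week 72 (hip".

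**The concern.** LOCF is accurate only if nothing relevant changes between the carried scan and the target visit. Here the carried scan is about half a year early. On the protocol's own account, hip loss on TDF-containing regimens is not finished at Week 24, so a carried hip value may not represent Week 48 loss. If the gap between TAF and TDF also changes after Week 24, the estimated Week 48 difference moves with the share of carried values.

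Two further features matter. Carried values enter the analysis as if measured at Week 48, with no allowance for the imputation. The companion observed-data analysis makes no use at Week 48 of the Week 24 scan of a subject who lacks a Week 48 scan. Neither planned analysis models the two visits together, although both scans are scheduled.

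At stake is the precision and, mildly, the accuracy of the BMD comparison. Hip BMD comes first in the fallback procedure of Protocol 8.3, with weight 0.4; spine follows with 0.2.

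**Working it through.** **1. Which scan can be carried.** The protocol synopsis schedules only one postbaseline DXA before Week 48, at Week 24. Protocol 6.3.2.2 requires an early-discontinuation scan only when none was done in the prior 24 weeks, so a subject with a Week 24 scan who stops before Week 48 normally gets no later one. SAP Table 3-4 sets the Week 24 window at Days 15 to 251 and the Week 48 window at Days 252 to 419. Baseline is not carried. Any value carried to Week 48 is therefore a Week 24-window scan.

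**2. The plan's own power figures (Protocol 8.8).** Inputs: 260 and 130 subjects, difference 1 point, SD 2.20 (hip) and 3.08 (spine), two-sided alpha 0.025 (critical z = 2.241).

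- Hip: SE = 2.20 × √(1/260 + 1/130) = 0.236. Power = Φ(1/0.236 − 2.241) = 97.7%. Section 8.8 states at least 90%, which is met.
- Spine: SE = 3.08 × √(1/260 + 1/130) = 0.331. Power = Φ(1/0.331 − 2.241) = 78.3%, against 77% stated.

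**3. Effect of LOCF on the hip difference.** Let m be the share of each arm with a Week 24 but no Week 48 scan, and f the fraction of the Week 48 gap already present at Week 24. With the same m in both arms and missingness unrelated to outcome:

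expected LOCF difference = 1.0 × [1 − m(1 − f)].

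The documents give neither m nor f; both are assumed. Power in brackets keeps n and SD as planned.

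| m | f = 0.5 | f = 1 | f = 1.25 |
|---|---|---|---|
| 5% | 0.975 (97.0%) | 1.00 (97.7%) | 1.012 (98.0%) |
| 10% | 0.95 (96.2%) | 1.00 (97.7%) | 1.025 (98.2%) |
| 20% | 0.90 (94.1%) | 1.00 (97.7%) | 1.05 (98.6%) |

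At f = 0.5 and m = 3% the difference is 0.985. For m from 3% to 10% the shift of 0.015 to 0.05 points is 0.06 to 0.21 standard errors (0.015/0.236 and 0.05/0.236).

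**4. The alternatives.** Under missing at random, a repeated-measures model targets 1.00 whatever f is. Its cost is an effective n divided by 1 + [m/(1 − m)](1 − ρ²), where ρ is the correlation between Week 24 and Week 48 changes. With ρ from 0.5 to 0.8 (assumed), hip power is 97.2–97.5%, 96.6–97.2% and 95.0–96.5% at m = 5%, 10% and 20%. Observed data alone give 97.0%, 96.2% and 93.9%.

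A simulation (3,000 runs, f = 0.5, ρ = 0.7, missing completely at random) gave mean differences of 0.949 for LOCF and 0.999 for a two-visit likelihood-type estimator at m = 10%, and 0.900 and 1.000 at m = 20%. Under that mechanism the observed-data estimate is also unbiased. The model's gain over it is precision, plus validity when the Week 24 result predicts who drops out.

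**5. Evidence on f.** Protocol 1.3.2 suggests continuing hip loss, but both arms of that study contained TDF. The only TAF-against-TDF BMD data are in Protocol Table 1-9 (HIV Phase 2 study). The Week 24 gaps there are −0.30 − (−2.103) = 1.80 points at the hip and −0.84 − (−2.48) = 1.64 at the spine, both above the 1.0 point assumed here for Week 48. Neither source fixes f.

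**6. China.** With at most 100 and 50 subjects, the hip SE is 2.20 × √(1/100 + 1/50) = 0.381, so a 0.05-point shift is 0.13 standard errors. DXA is done only at capable sites, so the SE would be larger and the ratio smaller.

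**The case against.** The strongest reply is that this changes nothing of substance. The shift is a small fraction of a standard error, the missing-data rates are assumed, and shrinkage would be conservative for a claim that TAF spares bone. The wide Week 48 window limits how often a value must be carried. An unimputed analysis is already planned, baseline is not carried forward, and Protocol 8.2.2 leaves room for further sensitivity analyses. The China SAP makes no between-arm BMD test, and its BMD mean plots with confidence intervals use observed data. SAP section 2 says the non-China Week 48 analysis has been done. The SAP for that analysis is not supplied, so nothing can be said about extra covariates or models in it. A repeated-measures model also has its own assumption, missing at random, and for subjects who stop drug it estimates the change expected had they continued like similar subjects.

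Most of this stands and limits the point to a low-cost improvement. It does not remove it: LOCF is right only when f = 1, and the observed-data analysis leaves scheduled information unused.

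A reader might infer that LOCF shrinks the BMD difference at both sites and always toward zero. The documents do not support that. The cited sentence puts spine loss by Week 24, compares two TDF-containing arms and gives no shape between Weeks 24 and 48. The HIV data show large gaps already at Week 24, though in another population and regimen and with no Week 48 value. A reader might also infer that the LOCF standard error is too small by a known amount. Imputation uncertainty is ignored, but nothing in the documents sizes it.

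**Conclusion.** The point holds in limited form. A missing Week 48 BMD value is replaced by a Week 24-window scan and treated as a Week 48 measurement. At the hip there is reason to think loss has not finished by then; at the spine the protocol gives no such reason.

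The effect on the TAF-TDF difference is likely small: 0.015 to 0.05 points of a planned 1.0 for 3% to 10% carried values if half the gap is present at Week 24, and 0.10 points at 20%. Hip power falls from 97.7% to between 97.0% and 94.1% for 5% to 20% carried. The estimate shrinks if the gap is still growing after Week 24, is unchanged if the gap is complete, and is enlarged if the gap is larger at Week 24. These figures rest on assumed m, f and ρ, equal missingness in the arms, and missingness unrelated to outcome for LOCF. No conclusion of the trial is shown to be at risk.

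**What to change.** Add to the SAP a prespecified repeated-measures model (MMRM) for percent change in hip BMD, and separately spine BMD, at Weeks 24 and 48. Include treatment, visit, treatment-by-visit and baseline BMD, and report the Week 48 difference with its confidence interval. Wherever a between-arm BMD difference is estimated, prefer this estimate to LOCF. Keep the LOCF and observed-data results as sensitivity analyses, and report by arm how many Week 48 values were carried forward.

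For the China Week 48 analysis, where BMD is descriptive, the model would be supportive. The completed non-China Week 48 analysis cannot be prespecified again; any rerun there should be labelled post hoc.

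The cost is a paragraph of SAP text and one standard model, with no new scans. The price is slightly more analysis work and reliance on missing at random, which the SAP should state.

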8.3. Multiplicity Adjustments

The primary hypothesis of non-inferiority between TAF 25 mg QD and TDF 300 mg QD with respect to the proportion of subjects with HBV DNA < 29 IU/mL will be tested first. If non-inferiority is established, then multiplicity adjustments will be performed for the secondary endpoints with a fallback procedure using the following weights:

- a) Hip BMD (weight = 0.4)
- b) Spine BMD (weight = 0.2)
- c) Serum creatinine (weight = 0.4)

8.4. Demographic Data and Baseline Characteristics

Demographic and baseline measurements will be summarized using standard descriptive methods by treatment group and overall.

Demographic summaries will include sex, race/ethnicity, geographical region, randomization stratification group, and age.

Baseline data will include a summary of body weight, height, body mass index, \log_{10} HBV DNA level, years positive for HBV, ALT level (\leq ULN, $>$ ULN), previous oral nucleoside/nucleotide treatment experience, previous interferon experience, and genotype.

8.5. Efficacy Analysis

8.5.1. Primary Analysis

The primary efficacy analysis will be conducted when approximately 390 randomized subjects complete 48 weeks of the double-blind treatment period or discontinue prematurely. A two-sided 95% confidence interval, based on the large sample theory adjusted for the randomization stratification factors (the adjusted Mantel-Haenszel proportions), for the difference (TAF – TDF) in the proportion of subjects who achieved HBV DNA $<$ 29 IU/mL will be used to compare the treatment groups. A non-inferiority will be declared if the lower bound of this confidence interval exceeds a non-inferiority margin of -0.10 . If non-inferiority is established, the lower bound of the 95% CI will be compared to 0; if the lower bound of the 95% CI is greater than 0, then superiority of TAF over TDF will be established using the same confidence interval. Details will be provided in the statistical analysis plan.

8.5.1.1. Justification of the non-inferiority margin

At Week 48 in study GS-US-174-0102, the proportion of subjects with HBV DNA $<$ 29 IU/mL in the TDF arm was 91.2%. At Week 48 in study GS-98-438, the proportion of subjects with HBV DNA $<$ 29 IU/mL in the placebo was 0%. The non-inferiority margin of 10% would preserve more than 88% of the lower bound of the 95% confidence interval of the difference between TDF and placebo.

	N _{TDF}	N _{PBO}	Response rate in TDF	Response rate in PBO	Difference	95% confidence interval lower bound
	250	61	91.2%	0%	91.2%	87.7%
Preserve at least 88% of lower bound						10%

Furthermore, at Week 48 in study GS-US-174-0102, the proportion of subjects with HBV DNA $<$ 29 IU/mL in the TDF arm was 91.2% and the proportion of subjects with HBV DNA $<$ 29 IU/mL in adefovir (ADV) arm was 56.0%. The non-inferiority margin of 10% would preserve more than 60% of the lower bound of the 95% confidence interval of the difference between TDF and adefovir (ADV).

	N _{TDF}	N _{ADV}	Response rate in TDF	Response rate in ADV	Difference	95% confidence interval lower bound
Study 174-0102	250	125	91.2%	56.0%	35.2%	25.8%
Preserve at least 60% of lower bound						10%

8.5.2. Analyses of Other Endpoints of Interest

Continuous secondary endpoints will be summarized using conventional descriptive statistics (n, mean, standard deviation, median, Q1, Q3, minimum, and maximum) by treatment group and overall. A Wilcoxon rank sum test will be used to compare the treatment groups, in an exploratory manner.

Categorical secondary endpoints will be summarized by number and percentage of subjects that meet the endpoint. A two-sided Mantel-Haenszel test, controlling for the randomization strata, will be used to compare the treatment groups, in an exploratory manner. Missing data will be handled by the missing = failure approach.

For the incidence of drug resistant mutations, the missing = excluded approach will be employed.

An analysis of the China subpopulation will also be conducted when approximately 150 randomized and treated China subjects complete 48 weeks of double-blind treatment or discontinue prematurely to examine the consistency of the responses between the China subpopulation and the overall population.

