- 12) Known hypersensitivity to study drugs, metabolites, or formulation excipients
- 13) Current alcohol or substance abuse judged by the investigator to potentially interfere with subject compliance
- 14) Any other clinical condition or prior therapy that, in the opinion of the investigator, would make the subject unsuitable for the study or unable to comply with dosing requirements.
- 15) Subjects on prohibited concomitant medications (See [Table 5-1](#)). Subjects on prohibited medications, otherwise eligible, will need a wash out period of at least 30 days.

Study Procedures/
Frequency:

Laboratory analyses (serum chemistry, liver tests, hematology, urinalysis, plasma HBV DNA levels, pregnancy testing [for females of childbearing potential]), vital signs, adverse events and concomitant medications will be performed at Screening, Baseline, and every 4 weeks thereafter through Week 48, every 8 weeks through Week 96, every 12 weeks through Week 144, and every 24 weeks through Week 384/Early Discontinuation (ED) visit. HBV serology (HBeAg and HBeAb, HBsAg and reflex HBsAb [anti-HBs]) will be performed at Screening and Baseline, HBsAg and reflex HBsAb will be performed every 12-16 weeks until Week 144, every 24 weeks until Week 384/ED and at Follow Up Weeks 12 and 24. Quantitative serum HBsAg will be assessed at Screening, Baseline, and every 12-16 weeks until Week 144, every 24 weeks until Week 384/ED, and at Follow Up visits. Bone and renal biomarker testing will be performed at Baseline and then at defined intervals (see Schedule of Assessments, [Appendix 2](#)) throughout the study. IL28B polymorphism genotype, HBV genotyping and vitamin D level will be performed at Baseline only. Fibrotest[®] will be performed at Baseline and every 48 weeks until

Week 384/ED. Fasting metabolic assessments (fasting glucose and lipid panel) will be conducted at Baseline, every 24 weeks until Week 240, and every 48 weeks until Week 384/ED visit.

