5. INVESTIGATIONAL MEDICINAL PRODUCTS

5.1. Randomization and Blinding

A centralized randomization procedure via an Interactive Voice/Web Response System (IVRS/IWRS) will be used for this study, whereby study treatment will be assigned to subjects according to the randomization schedule. A unique subject number will be provided during randomization. If the subject is deemed ineligible for this study by HBV serology (i.e. HBeAg-positive CHB), this information may be used to determine eligibility for GS-US-320-0110 (another Gilead Sciences Phase 3 study in HBeAg-positive, CHB subjects; this study must also be IRB/EC approved at the participating center). Eligible subjects will be randomized 2:1 to receive either blinded TAF 25 mg and TDF matched placebo or TDF 300 mg and TAF matched placebo for 144 weeks (96 weeks under Amendment 2.1). Subjects will be stratified by plasma HBV DNA level ($< 7 \log_{10}$ IU/mL, $\geq 7 \log_{10}$ IU/mL - $< 8 \log_{10}$ IU/mL, $\geq 8 \log_{10}$ IU/mL) and oral antiviral treatment status (treatment-naïve vs. treatment-experienced). At Week 144, all subjects will be switched to open label TAF 25 mg QD up to an additional 240 weeks (Week 144 through Week 384/ED). Subjects already assigned to open-label TAF 25 mg QD at Week 96 per Amendment 2.1 will continue on TAF through Week 384/ED. For the entire duration of the study, subjects and investigator will remain blinded to the initial treatment regimen to which the subjects were randomized.

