8.7.1. Biomarker Analysis

Selected bone biomarkers, including C-type collagen sequence (CTX) and procollagen type 1 N-terminal propeptide (P1NP), and selected renal biomarkers, including urine retinol binding protein, and urine beta-2-microglobulin, will be summarized by treatment group and visit using descriptive statistics. The difference in change from baseline in these biomarkers between two treatment arms will be tested using Wilcoxon rank sum test.

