3.3. Strata and Covariates

Randomization was stratified by plasma HBV DNA level ($< 7 \log_{10}$ IU/mL, $\geq 7 \log_{10}$ IU/mL - $< 8 \log_{10}$ IU/mL, $\geq 8 \log_{10}$ IU/mL) and oral antiviral treatment status (treatment-naïve vs treatment-experienced) at screening. HBV DNA strata will be reclassified using baseline HBV DNA level for stratified statistical analysis.

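### The continuous other endpoints and the bone and renal biomarkers are compared with an unstratified Wilcoxon test without a baseline covariate, unlike the plan's own handling of categorical endpoints and creatinine

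*Protocol*

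**What the plan says.** Protocol 8.5.2 gives the test for continuous endpoints: "A Wilcoxon rank sum test will be used to compare the treatment groups, in an exploratory manner". The next paragraph gives the test for categorical endpoints: "A two-sided Mantel-Haenszel test, controlling for the randomization strata, will be used to compare the treatment groups, in an exploratory manner". Both carry the same exploratory label; only the second uses the strata.

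Protocol 8.7.1 covers CTX, P1NP, urine retinol binding protein and urine beta-2-microglobulin: "The difference in change from baseline in these biomarkers between two treatment arms will be tested using Wilcoxon rank sum test". No strata, baseline covariate or exploratory label appears there.

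What an adjusted analysis needs is already available:
- Protocol 5.1: "Subjects will be stratified by plasma HBV DNA level" (three levels) and by oral antiviral treatment status (two levels).
- Protocol synopsis, biomarkers: "Bone and renal biomarker testing will be performed at Baseline and then at defined intervals".
- Protocol synopsis, FibroTest: "will be performed at Baseline and every 48 weeks until" Week 384 or early discontinuation.
- SAP 3.3: "HBV DNA strata will be reclassified using baseline HBV DNA level for stratified statistical analysis".

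The three key secondary endpoints are handled elsewhere. Protocol 8.6.1 analyses hip and spine BMD by ANOVA with treatment only, and serum creatinine by ANCOVA with baseline creatinine.

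The SAP supplied covers only the Week 48 analysis of subjects enrolled in China. It plans descriptive summaries for FibroTest (6.2.2), bone biomarkers (7.3.2) and renal biomarkers (7.4.5 to 7.4.7), and names no Wilcoxon test.

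**The concern.** Two neighbouring paragraphs of one section treat the strata differently without a stated reason. Their shared exploratory label cannot be that reason. Similarly, change in creatinine is adjusted for its baseline while change in a urine biomarker is not.

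Subtracting baseline is not the same as adjusting for it. A change score gives baseline a fixed coefficient of 1. When the true slope of follow-up on baseline differs from 1, baseline noise stays in the comparison, and so does part of any chance imbalance between arms. What is at stake is the precision of supporting comparisons. The protocol treats such markers as support: its account of the HIV Phase 2 study (1.2.4.6.3) uses bone turnover markers to back up the BMD results, and 1.3.3 reads biomarker changes as suggestive of better bone and renal tolerability.

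**Working it through.** **1. The plan's own figures.** No power is stated for any Wilcoxon comparison. The stated primary power of 90% reproduces: standard error = sqrt(0.91 × 0.09 × (1/260 + 1/130)) = 0.0307; 0.10/0.0307 − 1.96 = 1.29; power 90.2%. For creatinine (0.03 mg/dL, SD 0.12) the plan states 52%; I obtain 53% taking two-sided alpha as 0.025, which the text does not attach to that endpoint. The standardised effect, 0.03/0.12 = 0.25 SD, serves below only as a yardstick.

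**2. Variance ratio.** Let r be the correlation of baseline with follow-up, and k the follow-up SD divided by the baseline SD. Neither is given in the documents. For a linear model,

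variance (baseline-adjusted) / variance (change score) = k²(1 − r²) / (k² + 1 − 2rk).

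With k = 1 this becomes (1 − r²)/(2(1 − r)) = (1 + r)/2.

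| r | k | Ratio | Reduction |
|---|---|---|---|
| 0.5 | 1 | 0.75 | 25% |
| 0.7 | 1 | 0.85 | 15% |
| 0.8 | 1 | 0.90 | 10% |
| 0.9 | 1 | 0.95 | 5% |
| 0.8 | 1.25 | 0.5625/0.5625 = 1.00 | none |
| 0.7 | 1.5 | 1.1475/1.15 = 0.998 | 0.2% |

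The gain vanishes when rk = 1, because the regression slope then equals the coefficient of 1 that the change score already uses.

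**3. Power for a 0.25 SD effect, two-sided 0.05, k = 1.** At 260:130, 0.25/sqrt(1/260 + 1/130) = 2.327. With the Wilcoxon efficiency 3/π = 0.955 under normality, power = Φ(2.327 × sqrt(0.955) − 1.96) = 62%. Linear ANCOVA power = Φ(2.327/sqrt((1 + r)/2) − 1.96).

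| Analysis | r = 0.5 | r = 0.7 | r = 0.9 |
|---|---|---|---|
| Linear ANCOVA, 260:130 (Wilcoxon 62%) | 77% | 71% | 67% |
| Linear ANCOVA, 100:50 (Wilcoxon 29%) | 39% | 35% | 32% |

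Part of that gap is linear against rank, not adjustment: an unadjusted linear comparison at 260:130 already has 64%. The fair comparison stays with ranks. Simulating a rank ANCOVA on change with baseline (no strata, normal data, 3000 runs) at 260:130 gives 73% / 69% / 62%, against 62% / 63% / 61% for the plain Wilcoxon test, at r = 0.5 / 0.7 / 0.9. At r = 0.9 the rank gain is within simulation noise.

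**4. Strata alone.** If the strata explained an assumed 5%, 10% or 20% of outcome variance, a comparison with 78% Wilcoxon power would have about 80%, 82% or 87%. Nothing in the documents shows that HBV DNA level or treatment history predicts bone or renal markers, so this gain may be nil.

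**5. Validity.** Simulated rejection under no effect was 4.5% to 5.3% for the plain Wilcoxon test and 5.0% to 5.6% for ANCOVA with baseline and strata. Both are consistent with 5%.

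**6. Large effects.** For CTX at Week 24 the HIV Phase 2 study reports 39.2% (SD 79.2) against 94.8% (SD 107.9). At 260:130, 55.6/sqrt(79.2²/260 + 107.9²/130) = 5.2, or about 99.9% Wilcoxon power; at 100:50 it is about 88%.

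**The case against.** **The choice is defensible.** Biomarker changes look skewed, with unequal spread between arms, so a rank test is sensible. The sponsor's earlier HIV study used Wilcoxon tests for these markers, and repeating them keeps the results comparable. This stands as a reason to stay with ranks and still report the plain test. It is no reason to omit baseline and strata, which a rank analysis can include.

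**Little hangs on it.** This stands. Neither the 8.5.2 tests nor the biomarker tests appear in the multiplicity procedure of Protocol 8.3, and no sample size rests on them. A reader might infer that these comparisons carry the safety case for TAF. The documents put that case on hip BMD, spine BMD and creatinine (8.1.3, 8.3), none of which uses the Wilcoxon test.

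**The gain may be nil.** This stands as a limit. Equal variance cannot be taken for granted when CTX rose by 39% and 95% on treatment in the earlier study. For effects that large, extra precision hardly matters.

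**The timing limits it.** SAP section 2 says the non-China Week 48 analysis has been done, under a plan not among these documents; any refinement there cannot be checked, and changing that test now would be post hoc. The China SAP plans no test for these endpoints. Both facts limit where a change can apply. They do not alter the current text of 8.5.2 and 8.7.1.

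**Conclusion.** The point holds as a minor one about efficiency and consistency. The protocol uses the strata for exploratory categorical endpoints and baseline for creatinine, but uses neither as an adjustment for the continuous other endpoints and biomarkers, and gives no reason.

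Under equal variances and assumed r of 0.5 to 0.9, linear adjustment for baseline would cut the variance by 25% to 5%. In a rank analysis of a 0.25 SD effect at 260:130, that is roughly ten points of power at r = 0.5 and almost nothing at r = 0.9. With larger follow-up variance the gain can be about zero. These inputs are assumptions, so no single figure can be claimed for this trial.

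A reader might go further and call the comparisons biased or their p-values unreliable. The documents do not support that: randomisation protects the test, the biomarkers are tested on change from baseline, and simulated type I error is near 5%. Nor does any confirmatory conclusion change.

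**What to change.** In Protocol 8.5.2 and 8.7.1, or in the SAP for any comparison not yet analysed, name a rank ANCOVA: change from baseline compared between arms on ranks, with the baseline value as covariate and stratified by HBV DNA level and oral antiviral treatment status. State before unblinding how sparse cells among the 3 × 2 = 6 strata will be pooled. Report the plain Wilcoxon test beside it as supportive, which keeps comparability with the HIV Phase 2 results.

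A van Elteren (stratified Wilcoxon) test would bring the strata into line with the categorical analysis, but it does not adjust for baseline and so earns none of the (1 + r)/2 gain.

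Leave the completed non-China Week 48 analysis as it was specified; an adjusted version there should be labelled post hoc.

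Cost: about one sentence in each section, a pooling rule, slightly more analysis work in standard software, and no new data.
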